5.1.2. Multicenter, randomized, open-label, two arms, phase II/III clinical trial

- Once eligibility is confirmed and the subject consents for participation, he/she will be randomly assigned to the following two groups at 1:1.

① Group 1 (Control arm)

Treatment will be according to the 2014 Korean guidelines for the treatment of tuberculosis (19) and 2014 WHO guidelines (20). Treatment principles are summarized as follows.

- Combination of treatment regimen
 - Intensive phase regimen comprising four effective second-line anti-TB drugs (including an injectable) and pyrazinamide.
 - It is recommended that at least five active drugs be used, selected appropriately based on drug susceptibility testing (DST) results.
 - Example of regimen: pyrazinamide, a fluoroquinolone, cycloserine, prothionamide, and an injectable
 - Efforts should always be made to use a fluoroquinolone, preferentially use levofloxacin or moxifloxacin.
 - Cycloserine should be used preferentially, but when it is not possible para-aminosalicylic acid (PAS) could be used.
 - The medication like linezolid, delamanid, or bedaquiline can be added from the beginning of the treatment if the patient has a resistance to injectables. In addition, linezolid, delamanid, or bedaquiline can be used to fortify the regimen when the adverse drug reactions occur to other anti-TB drugs.
 - The usage and dosage follow 2014 Korean guidelines for the treatment of tuberculosis published by the Committee for the Revision of Korean Guidelines for Tuberculosis and the Korea Centers for Disease Control and Prevention (19) but not limited to it.

Type of Drug	Dose		
	Usual dose	Maximal dose	Usage
Ethambutol	15-20mg/kg	1600mg	Once, before or after

Confidential

MDR-END v14.0, 20Mar2020

			meal
Kanamycin Amikacin Streptomycin Capreomycin	15mg/kg, < 50 years 10mg/kg, ≥ 50 years	1000mg, < 50 years 750mg, ≥ 50 years	Once
Cycloserine	500mg, < 50 kg 750mg, 50-70 kg 750-1000mg, >70 kg	1000mg	Once or divide in two, before or after meal (best to take on an empty stomach)
Prothionamide	500mg, < 50 kg 750mg, 50-70 kg 750-1000mg, >70 kg	1000mg	Once or divide in two, after meal
PAS	150mg/kg	12g	Divide in two or three after meal

- Treatment duration

- Intensive phase is recommended to be a minimum of 8 months.
- Total treatment duration is recommended to be 20 to 24 months.

② Group 2 (Investigational Group)

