Regimen consists of only oral medication using delamanid, linezolid, levofloxacin, and pyrazinamide, for nine or twelve months.

- Treatment duration

- A total of 9 months (40 weeks) when sputum culture conversion to negative occurs within three months of treatment
- A total of 12 months (52 weeks) when sputum culture conversion to negative occurs between 3 and 6 months of treatment

- Combination of treatment regimen

- Delamanid, 200mg/day (100mg bid)
 - Use for the entire treatment period unless it must be stopped for reasons such as adverse events.
- Linezolid
 - 600mg/day during the first two months
 - 300mg/day afterwards until the end of treatment

Confidential

MDR-END v14.0, 20Mar2020

- If linezolid re-administration is required after temporary discontinuation due to adverse events, the dose reduction to 300mg is allowed even within two months of treatment.
- Levofloxacin
 - $\leq 50\text{kg}$, 750mg/day
 - $>50\text{kg}$, 1000mg/day
 - Can be reduced or substituted with moxifloxacin due to reasons such as adverse events, and at this time, QT prolongation should be observed closely. Also, this substitution will not be considered as a drug change since both are fluoroquinolones of similar potency.
 - Once a day
- Pyrazinamide
 - $<50\text{kg}$, 1000mg/day
 - 50-70kg, 1500mg/day
 - $>70\text{kg}$, 2000mg/day
 - Can be reduced due to adverse event. Even if pyrazinamide resistance is discovered on the phenotypic drugs susceptibility testing after commencing treatment, it can be continued (20).
 - Once or divide in two or three

Since the definition of treatment outcomes follows the 2014 WHO Guidelines (20), as described in the ‘Research Protocol 6. Definition’, the change of a drug is allowed according to medical judgments, such as adverse drug reactions. However, the change of two or more drugs is considered ‘treatment failed’ and the participants will be withdrawn from the study.

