6.4. Treatment Outcome Definitions

Definitions of treatment outcomes refer to 2014 WHO Guidelines (20). For investigational group, 6 months will be considered as intensive phase.

<Definitions of treatment outcomes for drug-resistant patients>

TREATMENT OUTCOME	DEFINITION
Cured	Treatment completed as recommended by the national policy without evidence of failure AND three or more consecutive cultures taken at least 30 days apart are negative after the intensive phase. ^a
Treatment completed	Treatment completed as recommended by the national policy without evidence of failure BUT no record that three or more consecutive cultures taken at least 30 days apart are negative after the intensive phase. ^a
Treatment failed	Treatment terminated or need for permanent regimen change of at least two anti-TB drugs because of: 
•Lack of conversion^b by the end of the intensive phase^a; or•Bacteriological reversion^b in the continuation phase after conversion^b to negative; or•Evidence of additional acquired resistance to fluoroquinolones or second-line injectable drugs; or•Adverse drug reactions.

Died	A patient who dies for any reason during the course of treatment.
Lost to follow-up	A patient whose treatment was interrupted for two consecutive months or more.
Not evaluated	A patient for whom no treatment outcome is assigned. (This includes cases “transferred out” to another treatment unit and whose treatment outcome is unknown).
Treatment success	The sum of Cured and Treatment completed.

^a For Treatment failed, lack of conversion by the end of the intensive phase[†] implies that the patient does not convert within the maximum duration of the intensive phase[†] applied by the programme. If no maximum duration is defined, an 8-month cut-off is proposed. For regimens without a clear distinction between intensive and continuation phases, a cut-off eight months after the start of treatment is suggested to determine when the criteria for Cured, Treatment completed and Treatment failed start to apply. (†For investigational group, 6 months will be considered as intensive phase.)

^b The terms “conversion” and “reversion” of culture as used here are defined as follows :

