8.3. Baseline Visit and Beginning of Treatment

- AFB smear microscopy, and MTB culture on liquid and solid media of sputum or bronchoscopic specimen will be performed.
- CXR, ECG, complete blood count, electrolytes, chemistry (albumin, total bilirubin, alkaline phosphatase, AST, ALT, Creatinine), anti-HIV antibody and HBsAg will be performed.
- Ishihara Test for Color-blindness will be performed to check baseline abnormalities of color blindness.

* Tests could be skipped in case of having available results or tests were performed recently within four weeks (In case of ECG, within a week).

* Study drugs can be administered before the obtaining of anti-HIV Ab, HBsAg, and alkaline phosphatase results since eligibility is not determined by these results.

* Administration of anti-TB regimen can begin at baseline visit since drug-resistant TB must be treated immediately.

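### Protocol 5.1.2 and the outcome table in 6.4 give different rules for when a change of two or more drugs is treatment failure, and 5.1.2 does not say which arm it binds

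*Combined protocol and SAP*

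**What the plan says.** The closing paragraph of Protocol 5.1.2, placed after the Group 2 drug list, begins "Since the definition of treatment outcomes follows the 2014 WHO Guidelines (20), as described in the" Definition section. It allows one drug to be changed on medical judgement and gives adverse drug reactions as an example. It then says "However, the change of two or more drugs is considered" treatment failed, "and the participants will be withdrawn from the study". No reason is attached to that sentence, and the change need not be permanent.

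The table in Protocol 6.4 defines failure as "Treatment terminated or need for permanent regimen change of at least two anti-TB drugs because of" one of four causes: no conversion by the end of the intensive phase, reversion in the continuation phase, "Evidence of additional acquired resistance to fluoroquinolones or second-line injectable drugs", or adverse drug reactions. Resistance already present in the enrolment strain is not on the list.

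For the control arm, Protocol 5.1.2 says "It is recommended that at least five active drugs be used, selected appropriately based on drug susceptibility testing (DST) results". For the investigational arm the four drugs are fixed, and pyrazinamide may be kept even if resistance to it is found later.

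Protocol 5.2 excludes failure from success and says that stopping a drug is not a drug change. Protocol 8.7 lists treatment failure as a reason for withdrawal. SAP 3.2 scores dropout for treatment failure during treatment as failure.

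**The concern.** Two rules in force give different answers for the same event, and the answer feeds directly into the primary outcome. The event can arise in ordinary control-arm care. Protocol 5.4 allows entry on a rapid genotypic rifampicin result, and Protocol 8.3 says "Administration of anti-TB regimen can begin at baseline visit since drug-resistant TB must be treated immediately". Phenotypic susceptibility testing is done on the first positive culture (Protocol 8.1) at outside laboratories, and cultures are incubated for six weeks (Protocol 8.5). A control participant may therefore start a regimen and later have two drugs replaced because the enrolment strain proves resistant to them. Table 6.4 does not call that failure; the literal wording of 5.1.2 does, and it ends participation.

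At stake is control-arm success in a non-inferiority comparison with a 10-point margin. Misscored control successes make the new regimen look better than it is. Withdrawal also means that the 24-month result of those participants may never be observed.

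**Working it through.** **1. One event under each rule.** A participant has two drugs permanently replaced because of resistance in the enrolment strain, without acquired resistance, adverse reaction, non-conversion or reversion.

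| Reading | Control participant | Investigational participant |
|---|---|---|
| Table 6.4 governs | not failure | not failure |
| 5.1.2 literal, both arms | failure, withdrawn | failure, withdrawn |
| 5.1.2 literal, Group 2 only | not failure | failure, withdrawn |

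**2. Exposure by arm.** Control regimens are meant to be fitted to susceptibility results. The investigational regimen is fixed, pyrazinamide may continue despite resistance, and participants with confirmed fluoroquinolone resistance are withdrawn (Protocol 8.7) and fall outside the SAP 3.1 mITT set. Susceptibility-driven changes in that arm should be few. Under the both-arms reading the bias would favour non-inferiority. Under the Group 2 reading only the investigational arm carries the unrestricted rule, so two-drug changes that are temporary or made for unlisted reasons count against it alone, and the bias runs against non-inferiority.

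**3. Whether later steps correct it.** The mITT set in SAP 3.1 removes only fluoroquinolone resistance, rifampicin mono-resistance and rifampicin susceptibility, so controls with other resistance stay in the denominator. The per-protocol set drops withdrawals before 80% of planned treatment, which removes such participants without recovering their outcome. Replacement (Protocol 10.1) covers only the first two weeks, shorter than the six-week culture.

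**4. The plan's own figure.** Inputs from Protocol 10.1: control 80%, investigational 90%, margin −10 points, one-sided α 0.025, power 80%. Unpooled formula:

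n = (1.960 + 0.842)² × (0.80×0.20 + 0.90×0.10) / (0.90 − 0.80 + 0.10)² = 7.849 × 0.25 / 0.04 = 49.06, so 50 per arm.

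The plan states 48, for which approximate power is 79.1%; this is close enough to use. 48/(0.50×0.95) = 101.05, so 102 per arm, as stated.

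**5. Sensitivity, both-arms reading.** Let f be the share of otherwise successful controls scored as failures through susceptibility-driven changes. The documents give no f, so these values are assumptions. Observed control success = 0.80 × (1 − f). The investigational arm is taken as unaffected, with true success 70%, exactly on the margin. The false-claim probability is the sum of binomial probabilities over all outcomes with 48 per arm for which the lower 97.5% Wald limit of the difference exceeds −10 points. The SAP names no interval method; Wald is assumed.

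| f | Controls affected (48 × 0.80 × f) | Control success | False non-inferiority |
|---|---|---|---|
| 0% | 0 | 80% | 2.7% |
| 2% | 0.8 | 78.4% | 4.0% |
| 5% | 1.9 | 76% | 6.8% |
| 10% | 3.8 | 72% | 14.1% |

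**6. Group 2 reading.** If the same assumed shares of otherwise successful investigational participants were affected, success would fall from 90% to 0.90×0.98 = 88.2%, 0.90×0.95 = 85.5% or 0.90×0.90 = 81%. The shift is of similar size in the opposite direction.

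**The case against.** The best defence is that 5.1.2 is shorthand. It cites the Definition section, uses that section's outcome term, and the one example it gives, adverse drug reactions, is on the 6.4 list. The primary outcome in Protocol 5.2 points to Section 6, not to 5.1.2. This reading is fair and may be what was intended. A reader might infer from the bare sentence that every two-drug change fails, whatever its cause; the documents do not say so. They also do not say that the 6.4 conditions limit the sentence, and it is the sentence that spells out withdrawal after a two-drug change, so sites could apply either.

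A reader might also infer that the bias must favour the new regimen. That holds only if the paragraph covers both arms, and its position after Group 2 leaves this open.

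The control-arm route is narrower than it may look:

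- The five-drug regimen is recommended, not required.
- Stopping is exempt, and how stopping one drug and adding another is classed is undefined.
- Susceptibility results may exist before treatment: entry can rest on phenotypic testing, existing results need not be repeated, and genotypic testing is done where available.

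Exposure is therefore limited to controls without earlier results whose strain resists at least two regimen drugs that are then replaced. All of this stands and limits the likely frequency. It does not remove the conflict.

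**Conclusion.** The conflict between Protocol 5.1.2 and 6.4 is in the text and concerns the primary outcome, so it should be resolved. Its effect cannot be sized from the documents. A reader might take a shift of 4 to 8 points (0.80×0.05 and 0.80×0.10) as the expected effect, but it only returns the assumed 5% and 10%, and the true share may be zero. What the sensitivity shows is leverage: with 48 per arm, about two misscored control successes would raise the false-claim rate at the margin from 2.7% to 6.8%. This assumes the both-arms reading, true rates of 80% and 70%, a Wald limit and an unaffected investigational arm. Confidence is high that the two rules differ, low on how many participants are affected, and the direction depends on which arm or arms 5.1.2 binds.

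**What to change.** Reconcile Protocol 5.1.2 with 6.4 so that one failure definition for the primary outcome applies identically to both arms. The reconciled text should state:

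- whether the four causes and the permanence condition in 6.4 limit the two-drug rule;
- how changes made because of susceptibility results on the enrolment strain are scored;
- whether replacing a stopped drug counts as a change.

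This review does not say which clinical or withdrawal rule is right.

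Record the reason for every drug change in the CRF. Re-check, by reason, outcomes already assigned under 5.1.2. A reason code cannot supply a 24-month result that was never observed, so where follow-up ended early, add to the SAP a sensitivity analysis of the primary outcome under each reading.

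The cost is a short protocol amendment, one CRF field, one added analysis and limited re-adjudication.

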2.2. Improvement of Treatment Efficacy

Even after treatment failure, MDR-TB patients live for several years and continuously spread MDR-TB bacilli to people they come in contact with. Considering this, it is necessary to raise the treatment success rate that is currently at 48~83.7% to solve the issues pertaining to MDR-TB.

It is expected that MDR-TB patient treatment success rate could be improved by using linezolid that was introduced to treat vancomycin resistant bacterial infection or using the newly developed anti-TB drugs like delamanid and bedaquiline. The biggest interest for now is on how to use it together with current anti-TB drugs.

In other words, the most urgent task is to investigate how to combine existing second-line anti-TB drugs such as fluoroquinolone, with the new drugs such as linezolid, delamanid and bedaquiline for treatment use.

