5.3. Secondary Outcomes

- Time to sputum *Mycobacterium tuberculosis* (MTB) culture conversion to negative (liquid and solid culture media)
- Sputum MTB culture conversion proportion at two months of treatment (liquid and solid culture media)
- Sputum MTB culture conversion proportion at six months of treatment (liquid and solid culture media)
- AE of grade 3 and higher
- Proportion of participants with a treatment success at the end of treatment.
- Proportion of relapse after treatment success (investigational arm)
- Proportion of death and time-to-death
- Comparison of treatment success rates between treatment groups according to pyrazinamide resistance.

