8.7. Withdrawal

- 1) When the investigator judges that participating in this clinical trial would not be in the best interests of the subject
- 2) When the subject withdraws consent
- 3) Treatment failure
- 4) When the subject becomes pregnant while on anti-TB medication.
- 5) When investigators get additional test results of resistance like below,
 - a) fluoroquinolone resistance (phenotypic or molecular method)
 - b) rifampicin monoresistance is confirmed
 - c) rifampicin susceptible

* Subjects who withdrawn from the study will receive the same treatment with other TB patients by standard of care treatment.

Confidential

MDR-END v14.0, 20Mar2020

9. Checking for Developing Resistance Against Study Drug

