- In order to test whether there is a statistical difference in sputum culture conversion proportions at six months of the treatment between the control arm and the investigational arm (liquid and solid culture media), each arm is summarized by conversion frequency and proportion, and the sputum culture conversion proportion at six months between the two arms are compared using the Chi-square test and Fisher's exact test.

4) Proportion of Treatment Success at the End of Treatment

- Summarize the frequency and proportion of treatment success at the end of Treatment in the investigational arm.

5) Proportion of Relapse after Treatment Success

- Summarize the frequency and proportion of relapse after the treatment success in the investigational arm.

Relapse is defined as mycobacterium tuberculosis (MTB) is cultured again at least two or more consecutive times, taken at least 4 weeks apart, after treatment success (excluding re-infection confirmed by other strains).

6) Proportion of deaths and Time-to-Death

- Summarize the frequency and proportion of death in the investigational arm and estimates the median survival time using the Kaplan-Meier method.

7) Primary Outcome Evaluation Between Treatment Groups According to the Pyrazinamide Resistance

- Presentation of treatment success rate in the control arm and the investigational arm in small groups according to the presence or absence of Pyrazinamide resistance, and verification of non-inferiority of treatment success rate difference between the treatment groups.

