Severity			
Mild, n	xx	xx	xx
Moderate, n	xx	xx	xx
Severe, n	xx	xx	xx

life threatening or disabling, n	xx	xx	xx
Death, n	xx	xx	xx
Relation			
not related, n	xx	xx	xx
doubtful, n	xx	xx	xx
possible, n	xx	xx	xx
probable, n	xx	xx	xx
definite, n	xx	xx	xx
Action taken			
No action taken, n	xx	xx	xx
Dosage Adjustment of study drug, n	xx	xx	xx
Suspension of study drug, n	xx	xx	xx
Permanent termination of study drug, n	xx	xx	xx
Unknown, n	xx	xx	xx
Not applicable, n	xx	xx	xx
Dosage adjustment of TB medication other than the study drug, n	xx	xx	xx
Suspension of TB medication other than the study drug, n	xx	xx	xx
Permanent termination of TB medication other than the study drug, n	xx	xx	xx
Outcome			
Resolved, n	xx	xx	xx
Resolved with residual effect, n	xx	xx	xx
Ongoing, n	xx	xx	xx
Death, n	xx	xx	xx
Unknown, n	xx	xx	xx

†† p-value by the Chi-square test ** p-value by the Fisher's exact test

1) p-value for comparison test of adverse reaction incidence rate between groups

2) In the case of an adverse reaction related to the drug used, the contribution of the drug is Possible, Probable, or Definite

3) p-value for comparison test of the incidence of adverse drug reactions between groups

4) p-value for comparison test of incidence of serious adverse events between groups

5) p-value for the comparison test for the incidence of grade 3 adverse events between groups

6) p-value for intergroup mortality comparison test

The analysis presents the adverse events occurring for each body system during the clinical trial period. The body system is classified according to SOC (System Organ Class) and PT (Preferred Term) of the MedDRA system. The adverse events are summarized for each severity of the body system, relation, and body system (Tables 24, 25, and 26).

Table 24. Adverse Events for Each Body System

		Investigational Arm (N=xx)	Control Arm (N=xx)	Total (N=xx)
mITT				
System Organ Class	Preferred Term			
SOC1		X	X	X
	XXX	X	X	X
	XXX	X	X	X
SOC2		X	X	X
	XXX	X	X	X
	XXX	X	X	X
PP				
System Organ Class		Preferred Term		

SOC1	X	X	X	
	XXX	X	X	
	XXX	X	X	
SOC2	X	X	X	
	XXX	X	X	
	XXX	X	X	
Safety				
System Organ Class	Preferred Term			
SOC1	X	X	X	
	XXX	X	X	
	XXX	X	X	
SOC2	X	X	X	
	XXX	X	X	
	XXX	X	X	

Table 25. Adverse Events for Each Severity of Body System

System Organ Class	Preferred Term	Investigational Arm (N=xx)						Control Arm (N=xx)					
		Severity						Severity					
		1	2	3	4	5	>=3	1	2	3	4	5	>=3
mITT													
SOC1		X	X	X	X	X	X	X	X	X	X	X	X

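### Treatment failure ends study participation with no planned vital-status follow-up to month 24, so later deaths are not systematically captured in the mortality outcome

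*Combined protocol and SAP*

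**What the plan says.** The last paragraph of the Group 2 description in Protocol 5.1.2 counts a change of at least two drugs as treatment failure "and the participants will be withdrawn from the study". Protocol 8.7 gives "3) Treatment failure" among its withdrawal reasons and does not restrict it to one arm. On what happens next, 8.7 says only: "Subjects who withdrawn from the study will receive the same treatment with other TB patients by standard of care treatment".

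Protocol 5.3 names "Proportion of death and time-to-death" as a secondary outcome. SAP 3.6.2 item 6 analyses it as follows: "Summarize the frequency and proportion of death in the investigational arm and estimates the median survival time using the Kaplan-Meier method". SAP 5.2.6 (Table 21) repeats this. Neither place gives a time window or a censoring rule. Separately, SAP 6.1 counts deaths by arm in Table 23, with footnote 6 reading "p-value for intergroup mortality comparison test".

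Under SAP 3.1, treatment failure does not remove a participant from the mITT set.

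**The concern.** A participant who fails leaves the study but remains in the mITT denominator. A death between failure and month 24 then has no planned route into the numerator. This follows from a stated rule, not from missing detail, and it can only lower the observed proportion of deaths.

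Time-to-death has the same gap. If withdrawn participants are censored when they leave, which is likely although the SAP does not say so, the censoring depends on treatment outcome and may be informative.

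At stake is how the trial describes mortality under a shortened four-drug regimen, in the single-arm Table 21 and in the two-arm comparison in Table 23. The primary outcome is not at stake, because a participant who fails is already a non-success.

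**Working it through.** **1. Following a participant after failure**

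| Place | What it provides after withdrawal for failure |
|---|---|
| Protocol 7.1, 7.2 and 8.4 (visit schedules) | No visits for withdrawn participants |
| Protocol 8.4.2 | Visits after end of treatment, investigational arm only, with smear, culture and chest X-ray; not directed at withdrawn participants |
| Protocol 8.7 | Routine care; no data collection |
| Protocol 10.2 item 2, SAP 3.2 | Classify the treatment outcome; collect no vital status |
| Protocol 11.2 | Follows serious adverse events unresolved at withdrawal until recovery, stabilisation or a similar end point |
| Protocol 13.2 | Consent text mentions keeping information for long-term follow-up; no procedure or endpoint uses it |

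Only Protocol 11.2 can bring in a later death, and only when a serious adverse event was open at withdrawal. Non-conversion or a two-drug change does not in itself meet the definition of a serious adverse event in 11.1.

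**2. The plan's own figure**

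The documents give no figure for deaths, so the evaluable sample size serves as the base. Inputs from Protocol 10.1 and SAP 2.3.1: success 80% control and 90% investigational, margin 0.10, one-sided alpha 0.025, power 80%.

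- n = [0.80 × 0.20 + 0.90 × 0.10] × (1.960 + 0.842)² / (0.90 − 0.80 + 0.10)² = 0.25 × 7.849 / 0.04 = 49.06, or 50 per arm after rounding up.
- The stated 48 is within two participants; power at 48 is 79.1%.
- Inflation: 48 / (0.50 × 0.95) = 101.05, rounded up to 102, as stated.

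The figure of 48 is a fair base.

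**3. Upper bound on unseen deaths**

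Formula: unseen deaths ≤ N × (1 − success rate) × q, where q is the risk of dying unseen by month 24. The documents give no q, so the values below are assumptions.

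- Investigational: 48 × 0.10 = 4.8 non-successes.
- Control: 48 × 0.20 = 9.6 non-successes.

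| q (assumed) | Investigational: deaths (points) | Control: deaths (points) |
|---|---|---|
| 10% | 0.48 (1.0) | 0.96 (2.0) |
| 30% | 1.44 (3.0) | 2.88 (6.0) |
| 50% | 2.40 (5.0) | 4.80 (10.0) |

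The percentage points do not depend on N. The absolute limits, at q = 100%, are 10 and 20 points.

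All of these are ceilings. Under Protocol 5.2, non-success also covers observed deaths, loss to follow-up, transfer out and relapse, so not every non-success is a withdrawn failure.

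**4. Direction between arms**

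At the planning rates the control arm has more non-successes and so could lose more deaths. Against this, Protocol 6.4 judges lack of conversion at 6 months in the investigational arm. For control, it proposes 8 months where no maximum is set, and 5.1.2 recommends an intensive phase of at least 8 months. Investigational non-converters may therefore leave about two months earlier. These effects pull in opposite directions, and the documents do not allow them to be netted.

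**The case against.** The strongest case against is that this is a modest gap in an outcome of limited weight. Protocol 10.2 and SAP 3.6.2 call the secondary outcomes exploratory. The planned Kaplan-Meier summary is a median, which would almost certainly not be reached at a planned non-success rate of 10%, with or without the missing deaths. These points stand, and they limit the importance of the finding. They do not remove the bias in the proportion of deaths or in Table 23.

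Several stronger readings are tempting, and the documents do not support them:

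- A reader might infer that deaths after failure are never counted. Protocol 11.2 still follows serious adverse events open at withdrawal, so some can be recorded.
- A reader might infer that the patients most likely to die are omitted. They stay in the denominator; only their later deaths may be missed. Protocol 2.2 says "Even after treatment failure, MDR-TB patients live for several years and continuously spread MDR-TB bacilli", which if anything suggests few deaths before month 24. Failure under 6.4 also includes regimen changes for adverse drug reactions, so some of these patients may be culture-negative.
- A reader might take the outcome category for death in Protocol 6.4, limited to the treatment course, as defining the secondary endpoint. It does not: Protocol 10.2 and SAP 3.2 consider death after treatment completion, and 11.2 counts deaths during the trial.
- A reader might infer that more failures would make the new regimen look safer. At the planning rates the ceiling is higher in the control arm, and the net direction is unknown.

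**Conclusion.** The point holds as a limited one. Participants withdrawn for treatment failure have no planned vital-status follow-up to month 24. Deaths in that interval are therefore not systematically captured, and the mortality summaries may be biased downward.

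With an assumed 10-30% risk of death by month 24, the upper bound is about 0.5-1.4 unseen deaths of 48 in the investigational arm and 1.0-2.9 of 48 in control. This rests on the planning success rates, on treating every non-success as a withdrawn failure, and on a mortality that the documents do not give. Nor do they state an expected overall mortality, so the loss cannot be compared with the quantity being estimated. The change is worth making because it is cheap and leaves treatment and the primary analysis untouched.

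**What to change.** - **Protocol 5.1.2 and 8.7:** separate stopping the assigned regimen from withdrawal from the study. For participants who leave because of treatment failure or by the investigator's decision, and who have not withdrawn consent, record vital status at month 24 by telephone or from the hospital record.
- **SAP 3.6.2 item 6 and Table 23:** define death as death from any cause from randomisation to month 24, including after treatment failure, with censoring at the last date known alive.
- **Unchanged:** the failure classification, the primary analysis and patient care.

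Cost: a protocol and consent wording change, and at most about 15 contacts or chart checks at the planning numbers (4.8 + 9.6 = 14.4). Some participants may be untraceable, and the reported death count may be slightly higher.
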